10. REFERENCES32

LIST OF ABBREVIATIONS AND RELEVANT DEFINITIONS

ABR	General Assessment and Registration form (ABR form), the application form that is required for submission to the accredited Ethics Committee; in Dutch: Algemeen Beoordelings- en Registratieformulier (ABR-formulier)
AE	Adverse Event
AP	Antipsychotic (medication)
AR	Adverse Reaction
BMI	Body Mass Index
CA	Competent Authority
CCMO	Central Committee on Research Involving Human Subjects; in Dutch: Centrale Commissie Mensgebonden Onderzoek
CRSWT	Cluster randomised stepped wedge trial
CV	Curriculum Vitae
CVD	Cardiovascular disease
CVR(M)	Cardiovascular risk (management)
DSMB	Data Safety Monitoring Board
EMR	Electronic medical record
EQ-5D-5L	EuroQoI 5 Dimensions 5 Levels questionnaire for quality of life
GCP	Good Clinical Practice
GDPR	General Data Protection Regulation; in Dutch: Algemene Verordening Gegevensbescherming (AVG)
GP	General practitioner/practice
IC	Informed Consent
MDM	Multidisciplinary meeting
METC	Medical research ethics committee (MREC); in Dutch: medisch-ethische toetsingscommissie (METC)
MHI-5	Mental Health Inventory
QRISK3	Predicted 10-year cardiovascular risk score
(S)AE	(Serious) Adverse Event
SF-36	36-item Short Form health survey for quality of life
SMI	Severe mental illness
Sponsor	The sponsor is the party that commissions the organisation or performance of the research, for example a pharmaceutical

company, academic hospital, scientific organisation or investigator. A party that provides funding for a study but does not commission it, is not regarded as the sponsor, but referred to as a subsidising party.

- TACTIC** Transmural collaborative care model for cardiovascular risk management and medication review for patients using antipsychotics
- UAVG** Dutch Act on Implementation of the General Data Protection Regulation; in Dutch: Uitvoeringswet AVG
- WMO** Medical Research Involving Human Subjects Act; in Dutch: Wet Medisch-wetenschappelijk Onderzoek met Mensen

SUMMARY

Rationale: The use of antipsychotic medication is increasing worldwide (1-3). It is well established that patients with a severe mental illness and patients treated with atypical antipsychotics have excess metabolic dysfunction (4) and are at an increased risk of cardiovascular disease (4, 5). Currently, monitoring of usage and effects of antipsychotic treatment (5-7), as well as cardiovascular risk screening in patients with severe mental illness or antipsychotic treatment (6) is not sufficient. General practitioners experience barriers regarding knowledge, collaboration with psychiatrists, and patient compliance (6). To overcome these barriers, the primary care cooperative Onze Huisartsen Arnhem BV developed in close collaboration with Radboudumc a transmural collaborative care model for cardiovascular risk management and medication review for patients using atypical antipsychotics in general practice (TACTIC). We have recently explored the feasibility of TACTIC in a pilot study (CMO 2020-7240) and used our findings to optimize the intervention for assessment of its effectiveness.

Objective: To assess the effectiveness of TACTIC regarding predicted cardiovascular risk and mental quality of life. The secondary objective is to assess its cost-effectiveness.

Study design: Incomplete cluster randomised stepped wedge trial.

Study population: Adult patients (>25yrs) from general practices, using atypical antipsychotics prescribed by their general practitioner.

Intervention: TACTIC is a one-time transmural intervention comprising three steps: 1) online information video to inform patients about the cardiovascular risks of antipsychotic use and about the procedures of the multidisciplinary meeting, 2) a multidisciplinary meeting with the patient to review his or her antipsychotic use and cardiovascular risk and to provide tailored treatment advice, and 3) a follow-up contact with the general practitioner to translate the treatment advice into an individualised action plan through shared decision making. TACTIC complements the current regular cardiovascular risk management programme for primary prevention of cardiovascular diseases of the primary care cooperative Onze Huisartsen BV that has been based on the specific guidelines of Dutch College of General Practitioners (NHG) and has been used in the Arnhem region since several years

Main study parameters/endpoints: Change in cardiovascular risk, as measured with the QRISK3 score, and change in mental quality of life, as measured with the MHI5 questionnaire.

Nature and extent of the burden and risks associated with participation, benefit and group relatedness:*Burden and risk associated with the intervention:*

Patients who are eligible and who want to participate in the study will be included in the regular cardiovascular risk management programme of the Arnhem primary care cooperative. This programme includes, according to current Dutch guidelines, 1 to 5 consultations with the GP and/or the practice nurse in which physical examination, i.e. measuring blood pressure and body weight, and blood and urine sample collection will take place. The frequency depends on the severity of the cardiovascular risk and the corresponding follow-up period. On top of the regular cardiovascular care patients who participate in the study will also receive the three-step TACTIC intervention. This is a one-time intervention. Patients who are eligible but who do not want to participate in the study will be included in the regular cardiovascular risk management programme, but will not receive the TACTIC intervention.

There is a potential risk associated with participation, as patients whose antipsychotic medication is altered during participation may destabilize mentally. However, this risk is expected to be low. Changes in medication will only take place after this advice has been given in *Step 2* (i.e. multidisciplinary meeting including the patient's GP, a psychiatrist, and the patient self) and has been followed in *Step 3* (i.e. shared decision making between the patient and his/her GP). The advice to change medication will only be given in *Step 2* as the psychiatrist, the GP, and the patient consider this option to be safe. Besides, the advice will only be followed in *Step 3* if both patient and GP feel safe with it. In addition, TACTIC contains precautionary measures to prevent destabilisation, i.e. any change in antipsychotic medication is accompanied with the advice of follow up consultations with the general practitioner or mental health nurse, and all patients who alter their antipsychotic medication will have a crisis prevention plan to ensure safety.

The potential benefit of participation is high, as changes in antipsychotic medication and appropriate cardiovascular risk screening and management will result in decreased cardiovascular risk.

Burden and risk associated with outcomes measurements:

Patients fill in questionnaires at baseline and every 5 months during follow-up. Based on our experiences in the pilot study, we expect that it will take approximately 20 minutes to fill in

the questionnaire. For the assessment of the primary outcome QRISK3 score routinely collected data from the cardiovascular risk management programme, i.e. blood pressure, body weight, smoking behaviour, and blood cholesterol and glucose levels.

INTRODUCTION AND RATIONALE

Antipsychotic medication is effective for a variety of psychiatric disorders, such as schizophrenia, bipolar disorder, schizoaffective disorder, or major depressive disorder. Remarkably, however, a large proportion of patients on antipsychotics do not have a diagnosis of a severe mental illness (6). Jakobs et al. found that, among patients in general practices who use antipsychotic medication, up to 68% did not have a registered diagnosis of a severe mental illness. These patients are using antipsychotics off-label. Reasons for off-label prescription can be anxiety, dementia, or sleep- and personality disorders.

The use of antipsychotic medication is increasing worldwide (1-3), but this is not without risk. It is well established that patients with a severe mental illness and patients treated with antipsychotics have excess metabolic dysfunction (4) and are at an increased risk of cardiovascular disease (4, 5). The increased risk of cardiovascular disease is multifactorial. Patients with a severe mental illness or on antipsychotic medication tend to have a high incidence of lifestyle risk factors, such as poor diet, lack of exercise, stress and smoking, besides possible genetic susceptibility (8, 9). Furthermore, there is evidence that people with severe mental illness are less likely to receive standard levels of care (5). Moreover, antipsychotics can cause weight gain, hypertension, glucose intolerance and dyslipidaemia, and can cause cardiac toxicity (10).

Although these factors may contribute as independent risk factors for cardiometabolic dysfunction and cardiovascular disease, having a severe mental illness itself is also an important independent risk factor (5), as well as antipsychotic treatment, particularly for certain drugs and for vulnerable patients (9). In a large prospective open cohort study in England, severe mental illness was associated with a 14% increased risk for women and a 13% increased risk for men (11). This was independent of the risk associated with atypical antipsychotics. Atypical antipsychotics were associated with an increased cardiovascular risk of 29% in women and 15% in men. In addition, antipsychotics cause a dose-related increased risk of sudden cardiac death (12). All in all, this results in a 8-20 years reduction in life expectancy (11).

In the Netherlands, it is common that psychiatrists initiate treatment with antipsychotic medication, but when patients reach a stable state, care is shifted to the general practice. This includes monitoring of treatment effects, adherence and side effects, as well as management of cardiovascular risk. However, monitoring of usage and effects of antipsychotic treatment as well as cardiovascular risk screening in patients with severe mental illness or on antipsychotic treatment is currently not sufficient (5-7). Lifestyle factors

are relatively easy to measure, but are barely considered for screening. Baseline testing of important physical parameters, prior to starting antipsychotic medication, is insufficiently performed (5). This is a serious aspect that needs to be addressed, even more since the adverse effects of antipsychotic medication may also impair the patient's adherence to treatment (13).

The increased cardiovascular risk in patients taking antipsychotic medications can be treated in a primary care setting, with lifestyle counselling as well as pharmacological interventions, in the same way as managing cardiovascular risk in other patient groups. The advantage of cardiovascular risk management in primary care is that general practices are very experienced in providing such care and are able to reach a broad population and detect the patients at risk. This also includes patients with mental disorders using antipsychotics who are in a stable phase and, as a consequence, are not under regular specialist care. However, general practitioners are generally not as familiar with the (long-term) side effects of antipsychotic use as psychiatrists, which may lead to a lack of follow-up. They often renew prescriptions that were initiated by the psychiatrist, without thorough check up. Furthermore, general practitioners and psychiatrists often do not collaborate in reducing cardiovascular risk in patients using antipsychotics. All healthcare professionals must learn to recognize the factors indicating antipsychotic-related cardiometabolic problems to prevent progression to type II diabetes, cardiovascular events and premature death (9).

To address both problems of potential overtreatment with antipsychotic medication and undertreatment of cardiovascular risk, we have developed a one-time transmural collaborative care model for structured antipsychotic medication review and cardiovascular risk management for patients in general practices (TACTIC). During TACTIC, the general practitioner closely collaborates with the patient, a carer (optional), a patient coach with lived experience, and a psychiatrist in a structured multidisciplinary meeting. This review results in tailored advice on antipsychotic treatment (continuation, lowering the dosage, switching to other medication, or discontinuation) and management of cardiovascular risk (e.g. losing weight, treatment of hypertension, regulation of cholesterol). Subsequently, the advice is converted to an individualised action plan through shared-decision making by GP and patient.

We have recently conducted a pilot study in which we assessed the feasibility of TACTIC (CMO 2020-7240). We followed three general practices who provided the TACTIC intervention to 28 patients in total. The feasibility appeared to be high. Based on the positive experiences and after the necessary adjustments in the procedures of the 3-step TACTIC

approach, the primary care cooperative decided to continue with TACTIC in an implementation process including a cluster randomised controlled trial. The pilot study was not powered nor designed to detect a statistically significant and clinically relevant difference, but did show a trend towards a positive health benefit regarding cardiovascular risk, particularly in patients with a moderate to high baseline QRISK3 score, i.e. score $\geq 5\%$. Pre-post analyses showed a decrease in predicted 10-year cardiovascular risk of 1.9% (SD 3.4) (*unpublished data*). Qualitative analysis, including individual interviews with patients and carers, and focus groups with healthcare professionals, gave us input to optimize the TACTIC procedures prior to assessing its effectiveness in the upcoming cluster RCT (*unpublished data*).

To our knowledge, TACTIC is the first intervention focussing on both medication review and primary prevention of cardiovascular disease in patients on atypical antipsychotic medication in general practice. With this study, we aim to contribute to better healthcare for this particular population, which is at a significantly higher risk of developing cardiovascular disease, but up until now seems to be forgotten in Dutch primary care.

1. OBJECTIVES

Primary objective: to assess the effectiveness of TACTIC in patients using atypical antipsychotics in general practice on cardiovascular risk and mental quality of life.

Secondary objectives: to assess cost effectiveness of the intervention TACTIC and its effectiveness regarding individual risk factors for cardiovascular disease.

2. STUDY DESIGN

We will conduct an incomplete cluster randomised stepped wedge trial including 32 general practices. Clusters (units of a general practitioner and his/her practice nurse) will be randomly allocated to four sequential steps over a 22-month period to implement TACTIC (Figure 1). Clusters will be randomised to time points at which they will receive the intervention. To minimize patient burden, data collection is not continuous, but undertaken on a selective number of occasions, which causes an “incomplete” stepped wedge design (14). Recruitment of clusters will start in September 2022, follow-up of the first step will start in March 2023. Follow-up of the last step will end in December 2024.

[figure not shown]

Fig. 1. Incomplete stepped wedge study design; rows are steps to which clusters will be randomised; columns are time periods of each 5 months.

3. STUDY POPULATION

3.1 Setting and population

This study will be conducted in the primary care cooperative 'Onze Huisartsen BV Arnhem'. This primary care cooperative serves around general practices with > 360,00 registered patients of whom approximately 4,000 patients use antipsychotics. Based on our pilot study we know that around 80 practices are sufficiently equipped to participate in our trial, i.e. they use the General Practice Information Systems Medicom or Promedico ASP and VIPlive, which are necessary for requesting digital consultations with the psychiatrist. A cluster is defined as a duo (or unit) of a general practitioner with his or her practice nurse. As a result, large general practices may provide multiple clusters when consisting of multiple duos.

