3.4 Sample size calculation

The sample size calculation is based on the following findings and expectations. Our pilot showed a reduction of the mean QRISK3 score of 1.9 points. This was after a follow-up period of 3 months, and under suboptimal intervention conditions, e.g. unclear expectation management, modified information meeting due to the corona pandemic. The standard deviation of the difference of QRISK3 score was 3.4 and the standard deviation of a single measurement was 12. This means there is a high reliability on patient level.

$$r_s = 1 - \frac{(SD_{diff}/SD)^2}{2} \approx 0.95$$

We expect that in the trial, after optimisation of the TACTIC procedures, we will be able to detect a reduction of a clinically relevant mean QRISK3 score of 2.5 points in the intervention group, compared to the control condition. Given an SD of 12, an intraclass correlation (ICC) of 0.10, and an α of 0.05, 500 simulated trials indicate that 32 general practices with each 12 patients are needed to provide a power of at least 80%. Given drop-out rates of 20% observed in our pilot study and less than 10% in a UK primary care study evaluating a comparable intervention (15), we include 15 patients per cluster. The required total number of participants will be 480 patients in 32 (or more) clusters.

This calculated sample size has also enough power to detect a clinically relevant improvement of 5 points on de mental health inventory, the mental domain of the SF36, which will be our second primary outcome.

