5.2 Randomisation, blinding and treatment allocation

Clusters will be randomised to either of the four steps, or cluster groups, as described in figure 1. The randomisation program we will use, will be custom made by an investigator with no clinical involvement in the trial. Blinding and treatment allocation are not applicable, as it is not possible to blind clusters.

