5.3 Study procedures

After enrolment of the general practice, a list with all eligible patients will be generated in VIPlive. A computerized programme will randomly select 30 eligible patients per general practice, who will receive a letter from their general practitioner, informing the patient about the upcoming trial. Patients will be invited to contact the general practice when they are interested in participation. An appointment for a regular cardiovascular risk management consultation at the general practice will then be made. Patients who did not reply to the letter, will be contacted by phone. In the context of the existing regional cardiovascular risk management programme patients will undergo physical examination (for measuring length, weight and blood pressure), venapuncture and urinalysis (for measuring risk factors, i.e. HbA1c, blood glucose, lipid spectrum and kidney function), and will be asked about their ethnicity, smoking status and family history of coronary heart disease. All other information will be derived from their medical file, e.g. having atrial fibrillation, migraines, or rheumatoid arthritis. In addition to the usual SCORE calculation, the QRISK score will also be calculated specifically for this study. When the QRISK3 score is below 5%, the patient does not meet the inclusion criteria and will be followed by the general practitioner according to the regular cardiovascular risk management

programme. Patients with a QRISK3 $\geq 5\%$ will be invited to sign informed consent for participation in the TACTIC intervention study.

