The MHI-5 consists of five questions with each six answer categories: continuously-mostly-often-sometimes-rarely-never. The answers of the positively formulated questions (questions 3 and 5) will be assigned the values 5, 4, 3, 2, 1, and 0, respectively. The

answers of the negatively formulated questions (questions 1, 2, and 4) will be assigned the values 0, 1, 2, 3, 4, and 5, respectively. Subsequently, a sum score will be calculated, multiplied by 4, resulting in an MHI-5 score ranging from 0 to 100, where a score of 100 equals perfect mental health.

Data analysis will be performed according to the intention-to-treat principle. Data from patients who discontinued follow-up will be included in the analysis up to the point of dropout. Descriptive analyses will be performed to describe the patient characteristics. Mean and standard deviation (std) or median and interquartile range for continuous characteristics and number and percentages for categorical characteristics will be determined. The relationship between treatment and outcome measures measured at 5, 10, 15, and 20 month follow up will be analysed with mixed three level linear or logistic regression, taking into account that the times of measurement are clustered within patients, and patients within general practices. We will perform a model with a random intercept and all other variables fixed. To test the effect of the intervention a model with time, group (intervention or control) and the interaction between time and group will be performed. A value of $p < 0.05$ will be considered statistically significant for all analyses, based on two-sided testing. Analyses will be performed using the Statistical Package for Social Sciences (SPSS, IBM Corp., Armonk, NY) version 25.

We will present QRISK3 scores and MHI-5 scores as means (SDs) for every measurement point, with notification of the number of patients included in the calculation.

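### Duos of general practitioner and nurse are randomised, but patients are invited and modelled by general practice, so a practice with several duos is under-invited and its randomised unit is missing from the model

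*Protocol*

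**What the plan says.** **Randomised unit.** Protocol section 3.1: "A cluster is defined as a duo (or unit) of a general practitioner with his or her practice nurse". The same section expects that "large general practices may provide multiple clusters when consisting of multiple duos". Section 5.2: "Clusters will be randomised to either of the four steps, or cluster groups, as described in figure 1". No rule links the allocation of duos that belong to one practice.

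**Size.** Section 2 describes an "incomplete cluster randomised stepped wedge trial including 32 general practices". In section 3.4 the simulation result is that "32 general practices with each 12 patients are needed". The section then sets the recruitment target at 15 per cluster and the total at 480 patients in 32 or more clusters.

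**Invitation.** Section 5.3: "A computerized programme will randomly select 30 eligible patients per general practice". QRISK3 screening (below 5% is not eligible) and informed consent come after the letter. No second draw of invitees is described.

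**Model.** Section 7.1 plans a three-level mixed regression, "taking into account that the times of measurement are clustered within patients, and patients within general practices". It names no duo level.

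**The concern.** Section 3.1 expressly separates practice from cluster, so the two words cannot be exchanged wherever a practice supplies more than one duo. Three things are then at stake.

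- **Recruitment.** The target is per duo but the supply of invitees is per practice. Each extra duo in a practice adds 15 to the target and nothing to the number invited.
- **Analysis.** The level at which treatment is allocated does not appear in the model. Variation between duos of one practice is then not credited to the unit that was randomised, and the standard error of the treatment effect can come out too small.
- **Separation of conditions.** A duo still in its control period can work in the same building as a duo already delivering TACTIC. Part of what TACTIC addresses (knowledge of antipsychotic side effects, contact with psychiatrists) is of a kind that colleagues could pass on.

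**Working it through.** **1. The protocol's own figures.** Inputs from section 3.4: 12 patients per unit, drop-out 20%, SD 12, SD of the difference 3.4, ICC 0.10, effect 2.5 points.

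- Inflation for drop-out: 12 / (1 − 0.20) = 15, and 32 × 15 = 480. Both agree.
- Patient reliability: 1 − (3.4/12)²/2 = 0.960; the protocol gives about 0.95.
- Power: the check used the generalised least squares variance for 4 steps of 8 clusters, 5 periods all measured, and a two-sided 5% test. With no patient correlation beyond the ICC, power is 0.784. That is within simulation error of 80%, since √(0.8 × 0.2/500) = 1.8 percentage points. With patient correlation 0.95 it is about 1.00.
- Figure 1 is not available, so the incomplete measurement pattern had to be assumed. Four trial patterns gave 0.60 to 0.71 without patient correlation and 0.87 to 1.00 with 0.95.

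**2. Yield needed from invitation.** Yield means the share of invitees who qualify and consent. Needed yield = 15 × duos / 30.

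| Duos in practice | Needed | Invited | Yield |
|---|---|---|---|
| 1 | 15 | 30 | 50% |
| 2 | 30 | 30 | 100% |
| 3 | 45 | 30 | 150% |

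If each invitee joins independently with probability y, the chance that a two-duo practice gets 30 of 30 is y³⁰: 0.1% at y = 0.80, 4% at 0.90 and 21% at 0.95. Even 12 per duo, the number before inflation for drop-out, needs 24/30 = 80%.

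**3. Effect on the total.** The number of two-duo practices is not given. Suppose 25%, 50% or 100% of the 32 clusters are in such practices:

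- 25%: (24 + 4) × 30 = 840 invited
- 50%: (16 + 8) × 30 = 720 invited
- 100%: 16 × 30 = 480 invited

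With one duo in every practice it would be 32 × 30 = 960. At an assumed 50% yield, participants number 420, 360 or 240 instead of 480.

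**4. Missing duo level.** The ICC of 0.10 was split, by assumption, into 0.05 for practice and 0.05 for duo, with 12 patients per duo and all 5 periods measured. The table gives the standard error (SE) that a model with a practice intercept only would report, against the true SE of its estimate.

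| Patient correlation | Two-duo practices | Reported SE | True SE |
|---|---|---|---|
| 0.95 | 8 or 16 | 0.223 | 0.223 |
| 0.50 | 8 | 0.686 | 0.699 |
| 0.50 | 16 | 0.680 | 0.703 |
| none beyond ICC | 8 | 0.861 | 0.997 |
| none beyond ICC | 16 | 0.822 | 1.050 |

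The understatement is nil at 0.95. At 0.50 it is 2% to 3% (0.686/0.699 = 0.98; 0.680/0.703 = 0.97). In the limiting case it is 14% to 22% (0.861/0.997 = 0.86; 0.822/1.050 = 0.78).

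**5. Different steps.** With 32/4 = 8 duos per step (equal steps assumed), the second duo of a practice has 7 of the 31 remaining places in the same step. The chance of different steps is 1 − 7/31 = 77%. The two duos are then in different conditions for at least one period.

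**The case against.** The strongest reply is that this is loose terminology. Sections 2 and 3.4 move between the two words with the same count of 32. If general practice in sections 5.3 and 7.1 simply means cluster, the shortfall and the missing level both vanish. That may be the intention. But section 3.1 draws the distinction explicitly, and a computer program will carry out the invitation rule, so the text still needs correcting.

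Several stronger readings are tempting and are not supported:

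- **The trial is sized by practice.** Only the simulation sentence and section 2 say practices. The target of 15 and the total of 480 are per cluster, and the allowance for more than 32 clusters leaves room to make up a shortfall.
- **A two-duo practice cannot reach its target.** It needs every invitee, which is out of reach in practice but not impossible. Strict impossibility starts at three duos.
- **The pilot's 28 patients in three practices foretell under-recruitment.** The protocol gives neither the number invited nor the target in the pilot. Scaling it up would give the same answer if every practice had one duo, so it says nothing about the unit.
- **Contamination dilutes the effect by a known amount.** The meeting and the action plan are specific to each patient, and a control duo's patients receive neither. A dilution figure requires inventing both the spill-over and the share of multi-duo practices.
- **The primary QRISK3 test is invalid.** At the protocol's own reliability the standard error does not change.

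A separate analysis plan could name the duo level. That would help, but section 7.1 has already fixed the levels and would then need to agree with it.

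**Conclusion.** The inconsistency is real and worth correcting; its consequences depend on how many practices supply more than one duo, which the protocol does not say. If none does, nothing is lost.

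- **Recruitment** is the firmest part. It follows from the text by arithmetic, provided the invitation rule is taken literally: 50%, 100% and 150% yield for one, two and three duos.
- **The model** omits the randomised unit. For QRISK3 this is a matter of correctness with almost no numerical effect. For the MHI-5, whose within-patient correlation is not given, the standard error could be understated: slightly at a correlation of 0.50, and more only if the correlation is much lower. These figures rest on the assumed equal split of the ICC and on complete measurement.
- **Spill-over** between duos of one practice is possible, because 77% of such pairs would be in different steps. Its direction is towards zero; its size cannot be stated from the protocol.

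**What to change.** 1. **Section 7.1:** fit a random intercept for the randomised duo, with general practice as a further level where a practice supplies more than one duo. This costs one line in the model. The practice variance may be poorly estimated if few practices have two duos.
2. **Section 5.3:** draw 30 eligible patients per cluster (duo) instead of per practice, as far as eligible patients allow. The needed yield is then 50% whatever the practice size. The cost is some extra letters. Whether each duo has 30 eligible patients should be checked: section 3.1 gives only about 4,000 antipsychotic users in the whole cooperative, before the eligibility criteria are applied.
3. **Sections 2 and 3.4:** use cluster throughout, and state that the simulated unit was the cluster if that is so. This is wording only.

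Optional, and only if randomisation has not yet been done: place all duos of one practice in the same step. This removes the side-by-side conditions, but it is a trade-off. The practice becomes the allocated unit, independent allocations fall below the number of duos, and step sizes become less even. The practice level in the model would then be essential. If randomisation is complete, items 1 and 3 still apply, and item 2 applies to any recruitment still to come.
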